10.2.7.3. Clinical Laboratory Testing

Blood samples for clinical laboratory tests, including hematology, serum chemistry and serology (including HIV, Hepatitis B, and Hepatitis C), will be collected at the time points specified in the Schedule of Events in [Section 2](#). Clinical laboratory tests performed are listed in [Section 11.1.7](#).

All clinical laboratory samples will be initially processed by site staff and shipped to a central laboratory for analysis as specified in the Laboratory Manual. An Investigator listed on the Form FDA 1572 will review all lab reports and document clinical significance for any out-of-range lab value(s) listed in the report.

10.2.7.4. Pharmacokinetic and Immunogenicity Sampling

Blood samples will be collected for ALD403 plasma PK and for determination of anti-ALD403 antibodies in serum (immunogenicity) at specified time points in the Schedule of Events in [Section 2](#). All samples will be initially processed, stored, and shipped as specified in the Laboratory Manual.

11. ASSESSMENT OF SAFETY

11.1. Adverse Events

11.1.1. Definitions

An adverse event (AE) is any untoward medical occurrence in a patient or clinical investigation participant administered a pharmaceutical product that does not necessarily have a causal relationship with the treatment. An AE can therefore be any unfavorable and unintended sign (including an abnormal laboratory finding), symptom, or disease temporally associated with the use of a medicinal (investigational) product, whether or not related to the medicinal (investigational) product. (ICH E6)

11.1.2. Assessment of Adverse Events

The Investigator is required to monitor the occurrence of adverse events for each subject from the time of informed consent through the course of the clinical trial. Adverse events may be reported by the subject, reported by a caregiver, or reported by the investigative site through Investigator site personnel open-ended questioning, through physical examination, laboratory test, documentation in medical records, or by other means. Adverse events include:

- Any new undesirable medical experience or an unfavorable and unintended change of an existing condition that occurs during or after treatment, whether or not considered related to the Investigational Product.
- Any abnormal assessment or laboratory findings considered by the Investigator to be clinically significant. Clinically significant findings include but are not limited to those that lead to discontinuation or interruption of study treatment, require therapeutic intervention, or require a change in subject management.

A new or worsening of a pre-existing or chronic condition is considered an adverse event and must be reported as such. Medical conditions, which existed prior to the time of informed consent into the clinical trial, will not be considered an adverse event unless the condition worsens. Unchanged, chronic, non-worsening or pre-existing conditions from the time of informed consent are not adverse events and should not be recorded on the AE eCRF.

Pre-existing medical conditions of clinical significance must be included in the subject's medical history and recorded on the medical history eCRF page.

Each event recorded on the AE eCRF is required to be assessed by the Investigator with regard to the following; seriousness, severity, and relationship to ALD403, as outlined below.

Seriousness

An adverse event or suspected adverse event is considered serious if in the view of either the Investigator or Alder, it results in;

- Death
- Is life-threatening (this means that the subject is at risk of death at the time of the event; it does not mean that the event hypothetically might have caused death if it were more severe)
- Inpatient hospitalization or prolonged existing hospitalization.
- A persistent or significant incapacity or substantial disruption of the ability to conduct normal life functions.
- Congenital anomaly/ birth defect
- Important medical events that may not result in death, be life-threatening or require hospitalization may be considered serious when, based upon appropriate medical judgement, they may jeopardize the patient or subject and/or may require medical or surgical intervention to prevent one of the outcomes listed in the definition (21 CFR 312.32(a) and ICH E2A).

Of note:

- A social hospitalization (i.e., hospitalizations for pre-admissions not due to an acute medical issue) is not considered an SAE.
- Hospitalization is considered a greater than 24 hour hospital admission.

Severity

The severity of an AE will be graded as follows:

- Grade 1 Mild; asymptomatic or mild symptoms; clinical or diagnostic observations only; intervention not indicated.
- Grade 2 Moderate; minimal, local, or noninvasive intervention indicated; limiting age-appropriate instrumental Activities of Daily Living (ADL).
- Grade 3 Severe or medically significant but not immediately life-threatening; hospitalization or prolongation of hospitalization indicated; disabling; limiting self-care ADL.
- Grade 4 Life-threatening consequences; urgent intervention indicated.
- Grade 5 Death related to AE.

Relationship to ALD403

The Investigator is required to assess the causality/relationship between each AE and the ALD403 as not related or related and record the assessment on the source documents and in the eCRF AE page. Medical judgment should be used to determine the likely relationship of the AE to the ALD403 considering all relevant factors including (but not limited to) relevant history, concomitant medical condition, and concomitant medications. Determination should be based on assessment of temporal relationships, biologic plausibility, association (or lack of association) with underlying disease, and presence (or absence) of a more likely cause.

Not Related: It is plausible that the AE has an etiology other than the ALD403 (e.g., pre-existing condition, underlying disease, concomitant medical condition, or concomitant medication).

Related: The AE cannot reasonably be explained by the subject's clinical state, concomitant\medical condition or concomitant therapies, and a temporal relationship exists between the event onset and administration of the ALD403.

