7.2. Clinical Trial Design

This is an open label trial of intravenous (IV) infusions of ALD403 in patients with chronic migraine. The trial will include two treatment phases. The primary treatment phase will include 4 infusions of ALD403 12 weeks apart. The secondary treatment phase will include up to 4 additional infusions of ALD403 12 weeks apart following the primary treatment phase.

Subjects who provide informed consent will be evaluated for eligibility based upon the inclusion and exclusion criteria. In the primary treatment phase, visits will occur on Day 0, Weeks 2, 4, 8, 12, 24, and 36 and subjects will receive 4 IV infusions of ALD403 on Days 0, Weeks 12, 24, and 36.

Subjects who receive all 4 infusions of ALD403 in the primary treatment phase may enter the secondary treatment phase. In the secondary treatment phase, subjects will receive up to 4 additional infusions for a total of 8 infusions. Visits and ALD403 IV infusions will occur on Weeks 48, 60, 72, and 84. Subjects will be followed for 20 weeks until Week 104 for a total study duration of approximately 106 weeks, including the screening period.

Subjects who don't receive all 4 infusions of ALD403 in the primary treatment phase or don't consent for participation in the secondary treatment phase will be followed at Week 48 and Week 56, at which point they will have their End of Trial visit.

Approximately 120 subjects will be enrolled and treated. Study specific assessments will be conducted according to the Schedule of Events presented in [Section 2](#).

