11.1.3. Recording Adverse Events

Event reporting will extend from time of informed consent until completion of the final visit.

Serious adverse events occurring after the end of the clinical trial must be reported if the Investigator considers there to be a causal relationship with ALD403.

An SAE Notification Form should be used to report any related SAEs which occur after the end of the clinical trial.

Adverse events (AEs) should be recorded on the AE eCRF, whether believed by the Investigator to be related or not related to the ALD403.

AE reporting should contain:

- A brief description of the event
- Date of onset
- Date of resolution
- Severity
- Actions taken or treatment required
- Relationship to Investigational Product
- Outcome
- Whether the event is considered serious

Whenever possible, the Investigator should group signs or symptoms that constitute a single diagnosis into a single event term. For example, “cough, rhinitis, and sneezing” might be grouped together as “upper respiratory tract infection.”

Asymptomatic abnormal findings considered by the Investigator to be clinically significant should be recorded as an AE, unless it is associated with a clinical syndrome that has already been reported as an AE.

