11.1.4. Reporting Serious Adverse Events

All SAEs that occur during the period of observation, whether considered to be related to ALD403 or not, must be reported within 24 hours of awareness or knowledge of the event. The

date the site personnel became aware of the serious adverse event must be recorded in the source document. To report the SAE, complete the eCRF AE page and indicate the reason for seriousness. The minimum information required for an initial report is:

- Sender of report (name, address of Investigator)
- Subject identification (screening/enrollment number, NOT subject name)
- Protocol number
- Description of SAE (e.g., event term)
- Seriousness criteria
- Relationship assessment

After receipt of the initial report, the Medical Monitor or designee will review the information and, if necessary, contact the Investigator to obtain further information for assessment of the event. Alder, or Alder's designee will be responsible for information processing and reporting in accordance with applicable local and regulatory requirements.

Alder will determine if an SAE requires expedited reporting to regulatory agencies. The clinical trial site personnel are responsible for reporting these events to their EC/IRB according to the institution's EC/IRB reporting requirements and in accordance with applicable local and regulatory requirements.

Should the EDC System not be available, serious adverse events must be reported on the paper SAE Notification Form. Additional details can be found in the Site Manual. This does not replace the EDC reporting system; information must be entered in the EDC system once the system returns to normal function.

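### Protocol 11.1.2 codes an adverse event Not Related once another cause is merely plausible, although its own guidance asks whether a more likely cause is present

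*Protocol*

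**What the plan says.** Protocol 11.1.2 (Relationship to ALD403) allows two answers for each adverse event: not related or related. It then gives two pieces of text.

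- **Guidance.** "Medical judgment should be used to determine the likely relationship of the AE to the ALD403". The factors named are timing, biologic plausibility, link (or no link) with underlying disease, and "presence (or absence) of a more likely cause". The list of considerations is expressly open.
- **Definitions.** "Not Related: It is plausible that the AE has an etiology other than the ALD403", followed by examples. "Related: The AE cannot reasonably be explained by the subject's clinical state" or by concomitant conditions or therapies, "and a temporal relationship exists between the event onset and administration of the ALD403".

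The protocol does not say which text governs when they disagree, and it gives no third category or default.

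The flag is used in these places:

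- SAP 3.6.1 tabulates study drug-related AEs and TEAEs.
- SAP 3.6.2.1 has one special-interest summary that uses relationship.
- Protocol 11.1.5 limits SUSARs to unexpected SAEs considered related.
- Protocol 11.1.3 says that SAEs arising after the end of the trial "must be reported if the Investigator considers there to be a causal relationship with ALD403".

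On-study reporting does not use it: "All SAEs that occur during the period of observation, whether considered to be related to ALD403 or not, must be reported within 24 hours".

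**The concern.** The two texts apply different tests to the same forced choice. The guidance is comparative: is something else more likely than the drug? The Not Related definition is not: is something else plausible? In a population with background prophylaxis (Protocol 9.3) and the comorbidities described in Protocol 5.2, a plausible alternative will often be available, so the lower bar could apply often.

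Long-term safety is the primary objective (Protocol 6.1), and every subject receives ALD403 (Protocol 7.2). Without a control group there is no within-trial comparison of event rates, so a reader of the results will look to the drug-related tables for attribution. Those tables would then depend on which of the two texts each Investigator followed. Two Investigators could code the same event differently, both within the protocol, and SAP 2.6.2 pools all sites.

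**Working it through.** The plan states no figure on this point, so the check sets the passages side by side.

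**Step 1. Grade the alternative cause.** Inputs: strength of the alternative (none; plausible but less likely than ALD403; more likely than ALD403) and temporal relationship (yes; no). This gives 3 × 2 = 6 cases. For this step I assume that a plausible alternative and a reasonable other explanation are the same thing. The guidance column is my reading of its factors, since it sets no threshold.

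| Alternative cause | Temporal relationship | Definitions, as written | Guidance factors |
|---|---|---|---|
| None | Yes | Related | Open, or favour related |
| None | No | Neither label | Favour not related |
| Plausible, less likely | Yes | **Not Related** | **Open, or favour related** |
| Plausible, less likely | No | Not Related | Favour not related |
| More likely | Yes | Not Related | Favour not related |
| More likely | No | Not Related | Favour not related |

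The conflict is in the third row. The drug is the likelier cause and the timing fits, yet the definition settles the call as Not Related. The second row has no label. These are logical cases, not event frequencies, and they do not measure impact.

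**Step 2. Drop the assumption.** Related names three sources of explanation (clinical state, concomitant condition, concomitant therapy). The list under Not Related is only illustrative. An event could therefore have a plausible cause outside those three, not be explained by any of them, and follow dosing. It would then meet both definitions. So the pair is not written as complements on either reading.

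**Step 3. Trace where the flag is used.**

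- The AE overview in SAP 3.6.1 has 7 items: TEAEs; drug-related TEAEs; serious TEAEs; TEAEs leading to treatment withdrawal, to treatment interruption and to discontinuation; deaths. One of the 7 uses the flag. The incidence tables by system organ class and preferred term also have a drug-related form.
- Of the 4 special-interest summaries in SAP 3.6.2.1, 1 uses it.
- SAP 3.6.2.2 says SAEs are summarised like TEAEs, without saying whether that includes a drug-related table.
- The overview in Protocol 13.4.4.1 has 4 items (AEs, SAEs, deaths, AEs leading to discontinuation). None uses the flag, so the drug-related outputs come from the SAP.
- The related-only rule in Protocol 11.1.3 applies after the final visit. Protocol 7.2 states "Subjects will be followed for 20 weeks until Week 104"; from the last scheduled infusion that is 104 − 84 = 20 weeks. For subjects who stop after the Week 36 infusion it is 56 − 36 = 20 weeks. Early withdrawals may differ.

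**Step 4. Test a partial repair.** Suppose the protocol only said that a plausible alternative is not enough for Not Related, and that anything failing Related is Not Related. The third-row event has a reasonable alternative explanation, so it still fails Related and falls back to Not Related by default. The Related definition has to change as well.

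**The case against.** The strongest reply is that 11.1.2 asks for medical judgement over all relevant factors, so the definitions are end labels for that judgement and not a mechanical rule. An Investigator who reads the section that way would code the third-row event on the balance of likelihood. This is a fair reading, and it shrinks the effect. It does not remove the problem, because the definitions as worded settle the case and nothing makes them subordinate to the guidance.

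Three stronger readings are tempting, and the documents do not support them.

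- **A reader might infer that the related count can only be equal or lower under the definitions.** The guidance sets no threshold, so there is no fixed count to compare with. Biologic plausibility can also cut the other way: it appears in neither definition, so an unexplained, well-timed but biologically implausible event is Related by definition, while the guidance could favour not related. Probably lower is as far as the text goes.
- **A reader might treat the event that fits neither label as a main defect.** It is nearly empty in practice. The list under Not Related is open, and an event with no temporal link to the drug will ordinarily have a plausible other cause.
- **A reader might infer that safety events would go unreported.** Protocol 11.1.3 records all AEs whatever their causality, and on-study SAEs are reported regardless of relationship. Even for SUSARs, Protocol 11.1.5 does not say whose causality judgement counts, the Medical Monitor or designee reviews initial reports, and the sponsor decides on expedited reporting (11.1.4). That is an exposure, not a demonstrated loss.

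**Conclusion.** The threshold mismatch stands and is worth correcting. Where the definitions are applied as written, a temporally related event for which ALD403 is the likelier cause is coded Not Related if another cause is plausible. The probable result is lower drug-related AE and TEAE counts and a shifted special-interest summary by relationship. There may also be an effect on which SAEs are treated as related for SUSAR purposes and after the end of the trial.

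The size cannot be derived: the documents give no event rates, no share of events with a plausible alternative, and no indication of which text sites will follow. All-cause AE, TEAE and SAE tables and on-study 24-hour reporting do not change.

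That the two definitions are not complements is a secondary point with small practical effect.

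**What to change.** Amend both definitions in Protocol 11.1.2 to the guidance's own standard.

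- **Related:** on the four guidance factors (timing, biologic plausibility, link with underlying disease, presence or absence of a more likely cause), ALD403 is judged a likely cause and no more likely cause is present. This replaces the condition that the event cannot reasonably be explained otherwise.
- **Not Related:** every other AE, with a statement that a plausible alternative alone is not sufficient.

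The pair is then exhaustive and mutually exclusive by construction. The SAP should state which definitions underlie its study drug-related outputs and footnote events coded before the amendment.

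The cost is protocol and eCRF-guideline wording, a site memo, one SAP sentence and a table footnote. No new data are needed. The downside is that the related count may rise and take in some background events, and coding before and after the change will not be fully comparable.

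Separately, SAP 3.6.3 ties the immune-response samples to a reaction the Investigator believes is related, while the collection sentence in Protocol 11.2 does not state that condition. This does not follow from the definitions, and the two passages should be reconciled on their own.

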11.1.3. Recording Adverse Events

Event reporting will extend from time of informed consent until completion of the final visit.

Serious adverse events occurring after the end of the clinical trial must be reported if the Investigator considers there to be a causal relationship with ALD403.

An SAE Notification Form should be used to report any related SAEs which occur after the end of the clinical trial.

Adverse events (AEs) should be recorded on the AE eCRF, whether believed by the Investigator to be related or not related to the ALD403.

AE reporting should contain:

- A brief description of the event
- Date of onset
- Date of resolution
- Severity
- Actions taken or treatment required
- Relationship to Investigational Product
- Outcome
- Whether the event is considered serious

Whenever possible, the Investigator should group signs or symptoms that constitute a single diagnosis into a single event term. For example, “cough, rhinitis, and sneezing” might be grouped together as “upper respiratory tract infection.”

Asymptomatic abnormal findings considered by the Investigator to be clinically significant should be recorded as an AE, unless it is associated with a clinical syndrome that has already been reported as an AE.

11.1.4. Reporting Serious Adverse Events

All SAEs that occur during the period of observation, whether considered to be related to ALD403 or not, must be reported within 24 hours of awareness or knowledge of the event. The

date the site personnel became aware of the serious adverse event must be recorded in the source document. To report the SAE, complete the eCRF AE page and indicate the reason for seriousness. The minimum information required for an initial report is:

- Sender of report (name, address of Investigator)
- Subject identification (screening/enrollment number, NOT subject name)
- Protocol number
- Description of SAE (e.g., event term)
- Seriousness criteria
- Relationship assessment

After receipt of the initial report, the Medical Monitor or designee will review the information and, if necessary, contact the Investigator to obtain further information for assessment of the event. Alder, or Alder's designee will be responsible for information processing and reporting in accordance with applicable local and regulatory requirements.

Alder will determine if an SAE requires expedited reporting to regulatory agencies. The clinical trial site personnel are responsible for reporting these events to their EC/IRB according to the institution's EC/IRB reporting requirements and in accordance with applicable local and regulatory requirements.

Should the EDC System not be available, serious adverse events must be reported on the paper SAE Notification Form. Additional details can be found in the Site Manual. This does not replace the EDC reporting system; information must be entered in the EDC system once the system returns to normal function.

11.1.5. Unexpected and Related Serious Adverse Events

Unexpected SAEs are those which:

- Are not previously reported as associated with ALD403, as referenced in the Investigator's Brochure.

- May be symptomatically and pathophysiologically related to an AE listed in the Investigator's Brochure, but differ from the event due to greater severity, frequency, or specificity.

Alder, or Alder's designee will report, to the appropriate regulatory authorities according to local and regulatory requirements, unexpected SAEs which are considered related to ALD403 (suspected unexpected serious adverse reactions [SUSARs]). The clinical trial site personnel are responsible for reporting these events to their EC/IRB in accordance with applicable local and regulatory requirements.

11.1.6. Follow-up of Adverse Events

Irrespective of the suspected causality, AEs will be monitored until resolution, stabilization in the judgment of the Investigator, or the subject is lost to follow up or withdraws from the trial.

